#### **Adverse Events Data Collection :**

At each evaluation time point adverse events will be assessed and only those related to the vaccine and donor lymphocyte infusion will be collected.

The donor and recipient will be provided a diary to collect any adverse events following administration of the vaccines and GM-CSF. The donor and recipient will bring the diary to each scheduled visit for review by research staff.

Adverse events related to the injection site and GM-CSF won't be capture unless these are considered serious. The data collection will reflect the onset and resolution date and maximum grade; beyond this point some events considered late complications post treatment might be recorded with the first date of its awareness and grade or resolution date when able to be documented.

Intermittent events should be labeled as such and followed until resolution. If a patient is taken off study while an event still ongoing, this will be followed until resolution unless another therapy is initiated. Pre-existing medical conditions will be recorded only if an exacerbation occurs during the active treatment period. Co-morbid events will not be scored separately.

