**E. Evaluation of Toxicity and Data Collection (Donors and Recipients)**

The severity of the adverse events observed in the proposed treatment will be graded according to the Common Terminology Criteria v3.0 (CTCAE).

Events not included in the CTCAE chart will be scored as follow:

General grading:

Grade 1: Mild: discomfort present with no disruption of daily activity, no treatment required beyond prophylaxis.

Grade 2: Moderated: discomfort present with some disruption of daily activity, require treatment.

Grade 3: Severe: discomfort that interrupts normal daily activity, no responding to first line treatment.

Grade 4: Life Threatening: discomfort that represents immediate risk of death.

Expected adverse events (AEs) related to the vaccine injection :

1. Local reactions (erythema, induration, swelling and tenderness),
2. Fever, chills,
3. Rash,
4. Myalgias and arthralgias.
5. Mild elevations in creatinine phosphokinase (CPK).

Expected adverse events (AEs) related to GM-CSF:

1. Fever, chills, diaphoresis
2. Myalgias, fatigue, malaise
3. Headache, dizziness
4. Dyspnea, bronchospasm, pleural effusion
5. Anorexia, indigestion, nausea, vomiting, diarrhea

6. Urticaria, rash, pruritus, hypersensitivity reactions
7. Bone pain
8. Thromboembolic events, phlebitis
9. Hypotension
10. Peripheral edema
11. Leukocytosis, thrombocytosis or thrombocytopenia
12. Hepatic enzyme abnormalities and bilirubin elevation have been recorded.

Expected adverse events (AEs) related to the vaccine:

1. Autoimmune reactions (hypogammaglobulinemia, collagen vascular diseases, cytopenias).
2. Local reactions

Expected adverse events (AEs) related to the DLI:

1. Graft versus host disease

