#### **Casualty Assessment:**

For the purpose of this study adverse events known to be caused by the vaccine administration, GM-CSF, donor lymphocyte infusion and to the vaccine and its direct consequences will be scored as definitive related.

Adverse events known to be related to drugs used for the treatment of Medical problems arise as direct consequences of known adverse events will be scored as probable related.

When the relationship of the adverse event cannot be ruled out with certainty the AE may be considered possible related.

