#### **Serious Adverse Event Reporting (SAE)**

A serious adverse event is – any adverse drug experience occurring at any dose that results in any of the following outcomes:

- Death
- A life-threatening adverse drug experience – any adverse experience

that places the patient, in the view of the initial reporter, at immediate risk of death from the adverse experience as it occurred. It does not include an adverse experience that, had it occurred in a more severe form, might have caused death.

- Inpatient hospitalization or prolongation of existing hospitalization
- A persistent or significant disability/incapacity – a substantial disruption of a person's ability to conduct normal life functions.
- A congenital anomaly/birth defect.

Important medical events that may not result in death, be life-threatening, or require hospitalization may be considered a serious adverse drug experience when, based upon appropriate medical judgment, they may jeopardize the patient or subject and may require medical or surgical intervention to prevent one of the outcomes listed in this definition. Examples of such medical events include allergic bronchospasm requiring intensive treatment in an emergency room or at home, blood dyscrasias or convulsions that do not result in inpatient hospitalization, or the development of drug dependency or drug abuse (21 CFR 312.32).

- Important medical events as defined above, may also be considered serious adverse events. Any important medical event can and should be reported as an SAE if deemed appropriate by the Principal Investigator or the IND Sponsor, the Investigational New Drug (IND) Office.
- All events occurring during the conduct of a protocol and meeting the definition of a SAE must be reported to the IRB in accordance with the timeframes and procedures outlined in "University of Texas M. D. Anderson Cancer Center Institutional Review Board Policy on Reporting Serious Adverse Events". Unless stated otherwise in the protocol, all SAEs, expected or unexpected, must be reported to the IND office, regardless of attribution (within 5 working days of knowledge of the event).
- All life-threatening or fatal events, expected or unexpected, and regardless of attribution to the study drug, must have a written report submitted within 24 hours (next working day) of knowledge of the event to the Safety Project Manager in the IND Office. -

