- The MDACC "Internal SAE Report Form for Prompt Reporting" will be used for reporting to the IND Office.
- Serious adverse events will be captured from the time the patient signs consent until 30 days after the last dose of drug. Serious adverse events must be followed until clinical recovery is complete and laboratory tests have returned to baseline, progression of the event has stabilized, or there has been acceptable resolution of the event.
- A research nurse will document information regarding the adverse event into the patient's/donor's medical record. The Study Chair will review and sign the documentation.
- Additionally, any serious adverse events that occur after the 30 day time period that are related to the study

treatment must be reported to the IND Office. This may include the development of a secondary malignancy.

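### Attribution decides whether non-serious cytopenias, low immunoglobulins and collagen vascular disease enter the adverse event record, and no summary of the scheduled blood counts and immunoglobulins is planned

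*Combined protocol and SAP*

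**What the plan says.** Three parts of Section 7.0 E bear on this.

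- **Collection.** Under Adverse Events Data Collection, "adverse events will be assessed and only those related to the vaccine and donor lymphocyte infusion will be collected". The same text adds: "Adverse events related to the injection site and GM-CSF won't be capture unless these are considered serious".
- **Expected harms.** The vaccine list opens with "Autoimmune reactions (hypogammaglobulinemia, collagen vascular diseases, cytopenias". Item 11 of the GM-CSF list reads "Leukocytosis, thrombocytosis or thrombocytopenia". Thrombocytopenia is a cytopenia, so it is covered by both lists.
- **Causality.** The definite category covers "adverse events known to be caused by the vaccine administration, GM-CSF, donor lymphocyte infusion and to the vaccine and its direct consequences", so GM-CSF events count as related. The lowest category reads: "When the relationship of the adverse event cannot be ruled out with certainty the AE may be considered possible related".

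Serious events are treated differently. They go to the IND Office whatever their cause, and important medical events may qualify by judgement; one example given is "blood dyscrasias or convulsions that do not result in inpatient hospitalization".

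Blood counts and immunoglobulins are scheduled repeatedly in donors (Sections 7.0 A and C) and recipients (7.0 B and D). Section 10 plans a mixed model of myeloma-specific CTLs, a survival regression and a stopping rule on grade 2-4 acute GVHD. It plans no adverse event table and no summary of the laboratory values.

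**The concern.** Causality is normally recorded beside an event. Here, for non-serious events, it decides whether the event is recorded at all, and the filter falls on harms that the protocol itself expects from the vaccine.

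There is no control arm, so an attribution made in a patient with several possible causes cannot be checked against unvaccinated patients. An event left out cannot be re-attributed later from the adverse event record. The formal stopping rule looks only at acute GVHD. Other harms rest on item 8 of Section 9.0, under which the study chair judges whether a toxicity pattern has become unacceptable. A filtered record is a less complete basis for that judgement.

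**Working it through.** The documents give no figure to reproduce, so the check follows one event through the rules.

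**1. Timing.** Donors are vaccinated at weeks -8, -6 and -2 (6.2) and recipients on the day of DLI and at weeks 4 and 8 (6.7). GM-CSF is given on days 0-3 of each of these three cycles (6.3, 6.10). Onset time therefore cannot separate the two agents.

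**2. One non-serious platelet fall in a recipient.**

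| Attributed to | Entered under 7.0 E? |
|---|---|
| Vaccine, alone or with GM-CSF | Yes |
| DLI, or GVHD caused by DLI | Yes |
| GM-CSF alone | No, although scored as definitely related |
| Myeloma | No |
| Tacrolimus or cyclosporine | No |
| GVHD already present before DLI | No |

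The last three causes are realistic. Section 4.0 requires persistent or relapsing disease for vaccine production. Section 6.4 allows low tacrolimus or cyclosporine levels and excludes GVHD only if it is uncontrolled.

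**3. Donors.** They do not have these competing causes. Their gap is chiefly non-serious thrombocytopenia ascribed to GM-CSF alone.

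**4. What narrows the gap.** The possibly-related category could keep many events in, but its wording permits that score and does not require it. The diary takes any event, but no text exempts diary entries from the filter, and a symptomless low platelet count or IgA would not appear in one. Serious event reporting ignores cause, but a non-serious event does not reach it.

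**5. Illustration only.** Let p be the all-cause rate of one named harm and m the share attributed to something other than the vaccine or DLI. Both are assumptions. With 10 independent recipients (the Section 10 maximum), the recorded rate is p(1 - m), and

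P(no recorded event) = (1 - p(1 - m))^10.

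For p = 0.20 and m = 0.50 the recorded rate is 0.10. The probability is 0.90^10 = 0.349, against 0.80^10 = 0.107 with full recording.

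| p | m = 0 | m = 0.25 | m = 0.50 | m = 0.75 |
|---|---|---|---|---|
| 0.10 | 0.349 | 0.459 | 0.599 | 0.776 |
| 0.20 | 0.107 | 0.197 | 0.349 | 0.599 |
| 0.30 | 0.028 | 0.078 | 0.197 | 0.459 |

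The table shows how easily a small trial can record nothing. It does not estimate what this trial would lose.

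**The case against.** The case for leaving the plan alone has real force.

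- **Attribution need not be exclusive.** Cytopenias are on the vaccine list. If timing cannot separate vaccine from GM-CSF, a vaccine relationship is hard to rule out, which points to the possibly-related score. This stands as a narrowing of the gap; the score remains discretionary.
- **The laboratory values exist.** Counts and immunoglobulins are drawn on schedule, and outside follow-up results go to research staff, so a later all-cause tabulation is possible. This stands. The loss is confined to the adverse event record and to planned reporting. Collagen vascular disease has no such laboratory series behind it.
- **No one promised an all-cause rate.** The only safety objective is the GVHD rate (Section 1.0, objective 2.2). This also stands, and it is a main reason for the low severity.
- **Ten recipients give little precision.** With no events in 10, the exact 95% upper limit is 1 - 0.025^(1/10) = 0.31. Recipients also receive DLI and their first vaccine on the same day, so a table cannot isolate the vaccine. Both are true, but neither is a reason to make the record selective.
- **Section 9.0 refers to toxicity observed.** Staff also see examinations, counts and diaries, so the effect on item 8 is a matter of completeness and not a failure of monitoring.

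A stronger reading is tempting. The protocol says: "Serious adverse events will be captured from the time the patient signs consent until 30 days after the last dose of drug". It then requires treatment-related serious events after that time to go to the IND Office. A reader might infer that late serious events from other causes drop out, and might count how many scheduled draws fall after the window. The documents do not support this. The same section requires all serious events during the conduct of the protocol to be reported to the IRB, with no stated limit on attribution or time, under an institutional policy that is not reproduced. Laboratory dates set against a window for serious events also say nothing about the loss of non-serious ones.

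**Conclusion.** The concern holds in a limited form. For non-serious cytopenias, hypogammaglobulinemia and collagen vascular disease, the adverse event record can understate all-cause frequency, mainly in recipients, and Section 10 plans no summary that would make this good. The size cannot be estimated from the documents; the probabilities above rest on assumed rates and shares.

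A reader might go further and infer that vaccine-caused harm is understated. That would follow only if events were wrongly attributed elsewhere, and nothing in the documents shows that they would be. Nor are the GVHD or CTL endpoints or the GVHD stopping rule affected. Severity is minor: a cheap improvement to a feasibility trial's safety record.

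**What to change.** In Section 7.0 E, record cytopenias, hypogammaglobulinemia and collagen vascular disease at every evaluation regardless of attribution, including when ascribed to GM-CSF, and keep attribution as a separate field.

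In Section 10, add one descriptive table, separately for donors and recipients who received at least one vaccine, showing:

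- CTCAE v3.0 grade shifts in blood counts from the value before the first vaccine;
- change in immunoglobulins from the same baseline at each scheduled draw. Recipients have IgG myeloma, so IgA and IgM should be their main measures, with IgG shown beside the M-protein from the same visit;
- counts of the named harms for all events and for those attributed to the vaccine or DLI, with exact 95% confidence intervals.

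The cost is a wording change, some extra event entries and one table; no new sample or visit is needed. The downside is that recipient counts will include events due to disease or immunosuppression and will look less favourable. Showing the attributed count beside the all-cause count lets the reader see both.

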## 6.0 Treatment Plan

### Idiotype Procurement

6.1 Recipient will undergo steady state plasmapheresis procedure to provide idiotype protein necessary to produce the vaccine. This is a standard procedure. Plasma (60-100 cc) from the plasmapheresis procedure will be sent to the MD Anderson Cancer Center GMP lab where it will be processed. The MDACC GMP lab will be responsible for producing the id-KLH conjugated vaccine according to the supplied standard operating procedure (see PDOL Appendices H and I). The vaccines will be kept in the GMP lab until requested. Alternatively vaccine can be produced using previously collected idiotype monoclonal protein collected on ongoing laboratory protocols and cryopreserved.

6.2 Donor will be vaccinated with an id-KLH vaccine 0.5 cc subcutaneously, once during weeks -8, -6, and -2 prior to donor lymphocyte collections.

The preferred site for the vaccine injection are the deltoid area (upper arm) and thigh. Sites should be alternated with each vaccine administration.

All donors will be observed in the clinic for two hours following vaccine administration. During the observation period, vital signs will be taken every 15 minutes during the first hour and then every 30 minutes during the second hour following vaccine administration.

6.3 GM-CSF 250 mcg/m^2 (dose rounded up to the nearest vial) S.C. will be given daily for four days (days 0-3) after each vaccine. All GM-CSF injections will be given in close proximity to the vaccination, as close to the exact site of injection as possible to ensure optimal recruitment of dendritic cells. The first dose of GM-CSF will be given by a nurse, and the remaining three doses will be given by the donor. Research staff will provide educational instructions regarding subcutaneous injection administration.

6.4 Recipient must meet the following criteria in order to receive the vaccine:

- Recipient to receive vaccine must be greater or equal than 3 months post allograft and with 5% or greater donor cell engraftment
- On a prednisone or prednisone equivalent dose of no more than 10 mg every other day at the time of registration, and with tacrolimus levels of <5 ng/dl or cyclosporine levels of < 100 ng/dl.
- Have no uncontrolled GVHD.

- Negative serum Beta HCG test in a woman with child bearing potential (not post-menopausal for 12 months or no previous surgical sterilization) and willing to use an effective contraceptive measure while on study.

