## **9.0 Criteria for Removal from the Study**

1. Patient/Donor withdrawal of informed consent
2. Patient death
3. Disease progression requiring anti-myeloma therapy
4. Patient/ Donor not being compliant
5. 5 years post donor lymphocyte infusion
6. If the recipient does not meet the "pre-vaccine" criteria in Section 7.0 B., the recipient and donor will be taken off the study.
7. Donor lymphocyte collection failure
8. An increasing or unexpected pattern of toxicity observed deemed unacceptable by the study chairman
9. Investigator judgment when the well being and best interest of the patient is compromised.
10. Inability of donor to provide lymphocytes after study registration

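### The adverse-event capture rule excludes non-serious injection-site and GM-CSF reactions that overlap with vaccine reactions it collects, so safety data on the regimen may be inconsistent or incomplete

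*Combined protocol and SAP*

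**What the plan says.** Under Adverse Events Data Collection in Section 7.0 E, events are assessed at each evaluation, but "only those related to the vaccine and donor lymphocyte infusion will be collected". The next paragraph provides a diary: "The donor and recipient will be provided a diary to collect any adverse events following administration of the vaccines and GM-CSF". Research staff review it at scheduled visits. The paragraph after that says: "Adverse events related to the injection site and GM-CSF won't be capture unless these are considered serious".

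Earlier in Section 7.0 E, the expected events of the vaccine injection begin with "Local reactions (erythema, induration, swelling and tenderness"), followed by fever and chills, rash, myalgias and arthralgias, and mild CPK elevation. The GM-CSF list repeats fever, chills, myalgias and rash. A further list, for the vaccine itself, contains autoimmune reactions (cytopenias among them) and local reactions again.

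Section 3-A describes GM-CSF as the adjuvant to the vaccine. On timing, Section 6.3 says that GM-CSF "will be given daily for four days (days 0-3) after each vaccine". On site, it says: "All GM-CSF injections will be given in close proximity to the vaccination, as close to the exact site of injection as possible". Section 6.10 makes the same provision for recipients.

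**The concern.** The capture rule depends on telling a vaccine reaction from an injection-site or GM-CSF reaction. The plan's own lists put several reactions in both groups, and the two products are given at nearly the same place over the same days. Two coordinators could handle the same non-serious fever or local reaction differently, and each could point to a sentence that supports the choice.

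The filter is seriousness, not grade. A grade 3 reaction that does not meet the serious-event definition can be left out if it is put down to the injection site or to GM-CSF.

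At stake is the description of how well people tolerate the regimen actually given, which is vaccine plus adjuvant. This weighs most for donors. They have no disease under treatment in this trial, and the only formal monitoring rule (Section 10.0, Toxicity Monitoring Rule) counts acute GVHD after lymphocyte infusion, which is a recipient outcome.

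**Working it through.** The plan states no figure on this point, so there is none to reproduce. The check compares the passages and counts.

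**1. Reactions listed for the vaccine injection (Section 7.0 E), set against the exclusion**

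| Reaction | Also an injection-site event or on the GM-CSF list? | Position under the rule |
|---|---|---|
| Local reactions | Injection-site event | Collected as vaccine-related and excluded as injection-site |
| Fever | GM-CSF list | Depends on attribution |
| Chills | GM-CSF list | Depends on attribution |
| Rash | GM-CSF list | Depends on attribution |
| Myalgias | GM-CSF list | Depends on attribution |
| Arthralgias | Neither | Collected |
| CPK elevation | Neither | Collected, if measured |

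So 1 + 4 = 5 of 7 reactions are exposed to the exclusion, and 2 of 7 are clear of it. One of those two, CPK, is not in the scheduled laboratory panels of Section 7.0 A and B. On the second vaccine list, cytopenias partly overlap with thrombocytopenia on the GM-CSF list.

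**2. Can attribution settle it?** The causality subsection of Section 7.0 E puts vaccine, GM-CSF and lymphocyte infusion together in its highest category of relatedness. It allows a possible relationship where one cannot be excluded. Suppose a fever on day 1 is scored as possibly related to the vaccine. It is equally possibly related to GM-CSF. The collecting sentence and the excluding sentence then both apply, and the plan does not say which prevails. Timing and site do not help: GM-CSF starts on the vaccine day, continues for three more days, and goes in beside the vaccine.

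**3. Does the diary close the gap?** It is meant to hold any event after vaccine or GM-CSF. No sentence says that its non-serious local or GM-CSF entries become study data, and the exclusion says they do not. Under Sections 6.3 and 6.10 the participant gives three of the four GM-CSF doses in each course, which would make the diary the main record made at the time on days 1-3. (Section 3-C instead has nursing staff give every dose; those passages need reconciling.)

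**4. Amount of exposure.** Section 10.0 sets a maximum of 10 treated patients. Donors and recipients each have three vaccinations.

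- Vaccine courses: 10 pairs x 2 people x 3 = 60.
- GM-CSF doses: 60 x 4 = 240.

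These are counts of exposure, not of lost events. Sixty is not a firm ceiling. Donors are vaccinated from week -8, and a pair leaves the study if the recipient fails the pre-vaccine criteria (Section 6.4) or collection falls short (Section 6.5), so more than 10 donors could be vaccinated.

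**5. What an empty row would mean.** As an illustration, suppose 10 donors, complete capture, and none with a given reaction. The one-sided 95% upper limit on its rate is 1 - 0.05^(1/10) = 0.26. With partial capture, even that wide limit is not justified, because an empty row may mean that the event was not entered.

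**The case against.** The case for leaving the text largely alone has substance. Omitting expected, non-serious reactions to a commercially sourced adjuvant is an explicit choice, and the background describes mild local reactions and well-tolerated GM-CSF. Vaccine tolerability is not among the objectives in Section 1.0. Pooling the attribution gives up some vaccine-specific information.

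Several stronger readings are tempting, and the documents do not support them.

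- *That the reported toxicity rate is biased toward zero.* No planned estimate uses these events. The toxicity definitions in Section 10.0 are GVHD, or GVHD or death, and are untouched. Any under-recording runs downward, but it affects a description.
- *That donor toxicity could not be seen.* Item 8 of Section 9.0 refers to "An increasing or unexpected pattern of toxicity observed deemed unacceptable by the study chairman". It asks for a pattern to be observed, not for a database signal. Donors have two hours of observation after each vaccine (Section 6.2), examinations, laboratory tests and toxicity assessments (Section 7.0 A), and diary review.
- *That every non-serious GM-CSF event is lost.* Cytopenias are also listed as vaccine events, possible relatedness may be scored, and the serious-event definition admits important medical events by judgement. Serious events are reported whatever their cause.
- *That tolerability is the only safety outcome donors contribute.* They also have tests at follow-up and yearly telephone calls (Section 7.0 C).
- *That the diary already holds everything.* A self-kept diary cannot detect a cytopenia.

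What remains is the conflict over local reactions, the overlap of four further reactions with no rule of precedence, and silence on how diary entries become data. Observing an event at the bedside does not put it in the study record.

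**Conclusion.** The point holds as a defect in the descriptive safety data. Read literally, the plan both collects and excludes non-serious local reactions, and it leaves non-serious fever, chills, rash and myalgias to an attribution for which it gives no rule. Non-serious events up to grade 3 can be missing or recorded unevenly in donors and recipients.

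Five of seven listed injection reactions are exposed. The number of events that would be lost cannot be derived, because the documents give no reaction rates by grade for this regimen. The conclusion assumes that staff follow the exclusion sentence as written, and that no data-entry instruction outside these documents overrides it.

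This should be corrected, chiefly for the donors' sake. It does not threaten serious-event reporting, the GVHD stopping rule or the primary aim.

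**What to change.** Reconcile the expected-event lists with the data-collection subsection of Section 7.0 E by replacing the exclusion sentence. The new text should provide that:

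- every grade 2 or higher event found in the diary, at a visit or in scheduled laboratory tests after a vaccine/GM-CSF course is entered, for donors and recipients, with onset, resolution and maximum grade;
- the event is attributed to vaccine plus GM-CSF as one regimen, with a vaccine-only attribution noted where it is clear;
- diary entries meeting this threshold are transferred to the study database at the visit where staff review them;
- results are summarised separately for donors and recipients.

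Grade 1 injection-site reactions may stay uncaptured.

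The change needs no new visit or test and alters no treatment. It costs extra data entry for about 60 vaccine courses if 10 pairs are treated, more if further donors are vaccinated whose recipients are not treated, and it yields a less favourable safety table. The grade 2 threshold is one workable choice. What matters is that a single stated threshold replaces the split by cause.
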